**Table 2: Sample Size Calculations**

		Prevalence of Outcome in Treatment Group		
		8%	10%	12%
		Two Batches		
Intracluster Correlation Coefficient (ICC)	0.005	760	1680	5560
	0.01	800	1760	5680
	0.05	880	1880	5840
	0.1	920	1920	5880
	Three Batches			
	0.005	720	1620	5400
	0.01	780	1680	5580
	0.05	840	1800	5700
	0.1	900	1860	5760
	Four Batches			
	0.005	720	1600	5360
	0.01	720	1680	5520
	0.05	800	1760	5680
	0.1	880	1760	5520

*Note:  $\alpha = 0.05$ , power = 80%, sampling structure = cross-sectional sample, sequences = 4, periods=5, number of periods of overlap between successive batches = 0, prevalence of outcome in control group = 14.8%*

## 6.0 DATA ANALYSIS

We will prepare a detailed statistical analysis plan (SAP) prior to completion of the trial which will provide a detailed description of all planned statistical analyses. Sections 6.1 to 6.5 provide a brief overview of the planned statistical approach.

### 6.1 Outcomes Analysis

The primary and secondary analyses will be conducted following intention-to-treat (ITT) principles, ensuring that participants are analyzed in their originally assigned treatment groups, regardless of adherence or protocol deviations. Reporting of the trial results will follow the 2010 CONSORT statement and the extension statements for a batched, stepped-wedge cluster randomized trial.

For the primary analysis of time to any all-cause return visits to emergency room or urgent care centers, we will perform a Cox proportional hazards regression model, with treatment included as the independent variable, and cluster pre-specified variables prognostic of the outcome, such as pre-injury work status, included as covariates. Results will be presented as a hazard ratio and corresponding 95% confidence interval (CI) (**Table 3**).

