## 3.0 TRIAL DESIGN

### 3.1 Description of the Trial Design

[figure not shown]
To efficiently and effectively address the above objectives, we have designed this trial as a batched stepped-wedge cluster randomized trial. The batched stepped-wedge cluster randomized trial is a pragmatic design commonly used in the evaluation of service delivery interventions. In the batched stepped wedge trial, clusters (in this case, surgeon clinics) of patients can be randomized and move through the trial design in ‘batches’ (e.g. a group of four clusters), which allows for flexibility in the timing of initiation of different clusters. The stepped wedge design itself begins with each cluster in the batch being given a date for crossover into the treatment group, in a randomly determined order. All clusters then enter an initial period in which no patients are exposed to the intervention. Subsequently, at regular intervals (“steps”), clusters cross from the control to the intervention under evaluation. This process continues until all clusters have crossed over to the intervention. At the end of the batch period there is a period when the intervention is being

implemented at all clusters. Data collection takes place throughout the batch period, so that all clusters contribute observations under both control and intervention observation periods. We will define a cluster as an individual orthopaedic surgeon fracture clinic.

We will conduct this trial in two to four batches, with four clusters in each batch. The number of batches will depend on the enrollment rates during the previous batches. For each batch, before participant enrollment begins, the Methods Centre will randomize the clusters (i.e. clinics) to determine when they will begin the intervention (i.e. social worker support in the fracture clinic). All clinics in the batch will begin participant enrollment into the non-intervention arm (i.e. usual care with no social worker services). At 10 weeks, one clinic will begin the intervention while the others will continue enrolling in the non-intervention arm as per randomization. At 20 weeks the second clinic will cross over to begin treatment, and at 30 weeks the third clinic will crossover. The fourth clinic will cross over after 40 weeks. All clinics (clusters) will enroll for 12 months.

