#### 5.0 SAMPLE SIZE

We chose our sample size to detect differences between the social worker intervention and usual care groups for all-cause visits to emergency room or urgent care centers (primary outcome). We estimated our sample size in accordance with the methodology of Kasza et al. using the R swdpwr package. For a binary outcome, the required cluster period size in a batched stepped wedge cluster randomized trial for a desired level of power depends on the number of time periods, number of clusters assigned to each sequence, number of sequences, number of batches, number of periods of overlap between successive batches, effect size, and ICC parameters. We will assume

80% study power with a two-sided Type I error rate of 5%, either two, three, or four batches of four sequences over five time periods, one cluster allocated to each sequence, no period overlaps, a 10% prevalence rate in the treatment group, a 14.8% prevalence rate in the control group, and a within-period intra-cluster correlation coefficient of 0.05. Based on these assumptions, we will require a total sample size of 1880 patients (cluster size of 47 patients per period) for two batches, 1800 patients (cluster size of 30 patients per period) for three batches, and 1760 patients (cluster size of 22 patients per period) for four batches. (**Table 2**). To account for a 10% loss to follow-up rate, the total sample size, regardless of the batch size, will be rounded to 2000.

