**Table 3: Primary Analysis Overview**

Objective	Outcome		Hypothesis	Method of Analysis
	Name	Type		
To determine if a dedicated social worker within the fracture clinic setting reduces all-cause return visits to emergency room or urgent care centers over 6 months	Any all-cause visits to the emergency room or urgent care centers	Binary	Participants receiving social work support will have fewer return visits to emergency room and urgent care centers in the 6 months following enrollment.	Cox proportional hazards regression model

For secondary analyses, we will follow mixed effects linear regression modelling for the LIMB-Q and satisfaction with care to account for repeated measures, with treatment, time of assessment, and pre-specified variables prognostic of each outcome included as independent variables in fixed effects. Each model will also include a cluster indicator as the random intercept. These secondary outcomes will be summarized as adjusted mean differences between groups with corresponding 95% CIs.

We will use logistic regression modeling for self-reported opioid use at 3 and 6 months using. Self-reported opioid use will be included as the dependent variable and each model will include the treatment variable, cluster, and pre-specified variables prognostic of the outcome as independent variables. We will present results as adjusted odds ratios with corresponding 95% CIs.

We will conduct a cost-effectiveness analysis from the payer's (hospital) perspective incorporating both participant utilities and direct healthcare costs and intervention costs. We will obtain health utilities from the EQ-5D. Costs will include the cost of employing a social worker, as well as healthcare use costs, such as fracture clinic visits, emergency room visits, urgent care facilities, and hospitalizations. We will compare these costs between the social worker intervention versus usual care groups using a cost-effectiveness analysis framework. The SAP will provide additional details on economic analysis plans.

We will also descriptively report the interactions made between the social worker and participants regarding the medium of contact, themes discussed, and the number and types of referrals made.

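### The primary Cox model, and every secondary model whose covariates are listed, leaves out calendar period, so a secular trend would be read as a social-worker effect

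*Protocol*

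**What the plan says.** **Design.** Section 3.1 describes a one-way stepped wedge. All four clinics in a batch start in usual care. "At 10 weeks, one clinic will begin the intervention while the others will continue enrolling in the non-intervention arm as per randomization", and the other three cross over at 20, 30 and 40 weeks. "All clinics (clusters) will enroll for 12 months". The sample size (Section 5.0) assumes, per batch, "four sequences over five time periods, one cluster allocated to each sequence, no period overlaps".

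**Models.** Section 6.1 lists covariates for three groups of models:

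- Primary outcome: "we will perform a Cox proportional hazards regression model, with treatment included as the independent variable, and cluster pre-specified variables prognostic of the outcome". The one example of a prognostic variable is work status before the injury. A conjunction seems to be missing; I read the list as cluster plus prognostic variables.
- LIMB-Q and satisfaction: mixed models "with treatment, time of assessment, and pre-specified variables prognostic of each outcome included as independent variables in fixed effects", plus a random intercept for cluster.
- Opioid use: "each model will include the treatment variable, cluster, and pre-specified variables prognostic of the outcome as independent variables".

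The third sensitivity analysis in Section 6.2 repeats the mixed-model list. The other two sensitivity analyses follow the primary model, and the subgroup analyses in Section 6.3 use the same type of Cox model. For missed visits Table 4 names only a negative binomial model, without covariates, and economic detail is left to the SAP.

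**The concern.** In each batch the first period is entirely usual care and the fifth entirely intervention. In between, the share of clinics on the intervention only rises. Anything that changes emergency or urgent-care use over the year is therefore correlated with treatment: season, access to urgent care, staffing, clinic practice. What separates the intervention from such changes in a stepped wedge is the comparison, within the same period, of clinics that have crossed over with clinics that have not. That comparison is used only if period is in the model.

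No listed model has it. The time variable in the mixed models is there to handle repeated measures, so it is the follow-up visit (6 weeks, 3 months, 6 months after consent), not the calendar step at which the patient was enrolled. Without period, the randomised crossover order does not protect the estimate. The hazard ratio can be biased in either direction, and the two-sided 5% error rate is not held if there is any trend.

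**Working it through.** **1. How strongly treatment and calendar time are tied.** Take T = 5 equal periods and a clinic with c control periods.

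- Mean control period = (1 + c)/2. Mean intervention period = (c + 1 + T)/2.
- Difference = T/2 = 2.5 periods, the same for all four sequences.
- With cluster as a fixed effect or stratum and period omitted, a linear trend of d per step therefore biases the effect by 2.5 × d. On the 52-week schedule this is 26 weeks of trend.
- Ignoring cluster altogether, the mean periods are 4.0 and 2.0, so the factor is 2.0. A random intercept for cluster gives a value between 2.0 and 2.5.
- The vanguard clinics (three 10-week periods) have T/2 = 1.5.

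**2. Does the sample size rest on the same omission?** Inputs from Section 5.0: "a 10% prevalence rate in the treatment group, a 14.8% prevalence rate in the control group", ICC 0.05, two-sided 5%, 80% power, cross-sectional sampling. The between-period ICC is not given and is set equal to 0.05. The method is a generalised least squares information matrix for the cluster-period means. Adding one patient per cluster-period changes the total by 40, 60 or 80.

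| Batches | Stated N | No period effects (identity / logit) | With period effects (identity / logit) |
|---|---|---|---|
| 2 | 1880 | 1840 / 1880 | 4880 / 4960 |
| 3 | 1800 | 1800 / 1860 | 4740 / 4800 |
| 4 | 1760 | 1760 / 1840 | 4640 / 4720 |

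At the stated 47, 30 and 22 patients per cluster-period, power is 79.8–80.9% without period effects and about 43–44% with them. The stated figures are matched, exactly or within one step, only when period effects are absent.

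**3. Bias and type I error on the risk scale.** Three batches, 30 per cluster-period (1800 evaluable), ICC 0.05, no period terms: SE = 0.0180. With bias b, the rejection rate under no effect is Φ(−1.96 + b/SE) + Φ(−1.96 − b/SE).

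- d = 0.5 points per step: b = 2.5 × 0.005 = 0.0125; b/SE = 0.69; rejection about 11%.
- d = 1 point per step: b = 2.5 × 0.01 = 0.025; b/SE = 1.39; rejection about 28%. Against the planned effect of 14.8 − 10 = 4.8 points, 2.5/4.8 = 52%.

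**4. Check on the hazard scale, true hazard ratio 1.** The expected estimate without period is the per-step hazard ratio to the power 2.5.

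| Fall in hazard per step | Expected HR | Simulated HR without period | False positives without period | With period |
|---|---|---|---|---|
| 5% | 0.95^2.5 = 0.88 | 0.88 | 13.5–16% | HR 1.00, 5–6% |
| 8% | 0.92^2.5 = 0.81 | 0.82 | 29.5% | HR 1.00, 5–6% |
| 10% | 0.90^2.5 = 0.77 | 0.77 | 46% | HR 1.00, 5% |

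The 5% row combines two simulations. One is a Cox model stratified by cluster (400 runs), which also gives the 8% row. The other is a piecewise-exponential model with cluster fixed effects (1500 runs; two batches, 47 per cluster-period, assumed between-cluster log-hazard SD 0.3), which also gives the 10% row. With no trend, the second simulation holds about 5% with or without period.

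**The case against.** The strongest reply is deferral. Section 6.0 calls what follows a brief overview and promises a detailed SAP, the list of prognostic variables is open, and nothing excludes period. That would suffice if the protocol were silent. It is not: it gives covariate lists that name cluster and, for the mixed models, a time variable, but not the term that this design needs. The sample size points the same way. An SAP that added period would contradict the stated 80% power; one that followed the protocol would leave the estimate confounded.

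Four further points stand, and they limit the wording:

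- The negative binomial and economic analyses list no covariates, so there period is unstated rather than left out of a list.
- The inference from Table 2 is not exact. No single link function reproduces every cell, and the between-period ICC had to be assumed. Still, no version with period effects comes near the stated totals.
- The factor 2.5 applies to full-batch clinics; it is 1.5 for the two vanguard clinics.
- The drift sizes are illustrative. One point per step means 4 points from the first to the fifth period, in the same direction in every batch. Seasonal effects could partly cancel if batches start at different times of year. Nothing in the plan ensures this, and a steady change in access or practice would not cancel.

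**Conclusion.** The concern holds. As written, the primary Cox model, the LIMB-Q, satisfaction and opioid models, and the sensitivity and subgroup analyses built on them estimate a before/after contrast within clinics. A linear trend enters at 2.5 times its per-step slope in full batches, so modest drifts are enough to matter: about 11% type I error at 0.5 points per step and about 28% at 1 point. The direction of any trend is unknown, so a real benefit could be hidden as easily as a false one produced.

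The factor 2.5 follows from the design, with equal periods and cluster adjustment. The error rates also rest on the assumed drift and on 1800 evaluable patients in three batches; the power and sample-size figures assume equal within- and between-period ICC of 0.05. The vanguard clinics were not modelled. The omission needs correcting before analysis, since it decides whether the primary result has the protection of randomisation.

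**What to change.** In Sections 6.1 to 6.3, state the primary model as treatment + batch-specific enrolment period (the 10-week step) + cluster + named prognostic covariates. Period can enter as fixed effects or as strata of the Cox baseline hazard. Add the same period term, keeping cluster, to every secondary, sensitivity and subgroup model, including the negative binomial model for missed visits. Make clear that the assessment-time term in the mixed models is the follow-up visit and does not replace enrolment period.

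The model change costs protocol and SAP wording only; enrolment dates and crossover dates give the period. The consequence is not free. Confidence intervals will be wider, and Section 5.0 and Table 2 must be recalculated with period effects and a stated between-period ICC. Under the assumptions above, 80% power needs about 4640–4960 patients, against the planned 2000. The sponsor will have to enlarge the trial, change the design or restate the power.

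### The covariate list of the primary Cox model is garbled: cluster is not clearly its own term, and no calendar-time term is listed on any reading

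*Protocol*

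**What the plan says.** Section 6.1 of the protocol gives the primary model as a Cox regression with treatment as the independent variable "and cluster pre-specified variables prognostic of the outcome, such as pre-injury work status, included as covariates". Table 3 adds only the name of the model. No stratum, frailty, fixed effect or robust variance for cluster is mentioned for this analysis, and no period or calendar-time term.

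Other models are clearer about cluster. For opioid use, Section 6.1 says that "each model will include the treatment variable, cluster, and pre-specified variables prognostic of the outcome as independent variables". The LIMB-Q and satisfaction models have a cluster random intercept, and so does the all-visits sensitivity model in Section 6.2. The time variable in those repeated-measures models is the follow-up assessment, not the calendar period of enrolment.

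Section 5.0 treats clustering as material: it assumes "a within-period intra-cluster correlation coefficient of 0.05", with "either two, three, or four batches of four sequences over five time periods, one cluster allocated to each sequence, no period overlaps". The first two sensitivity analyses (Section 6.2) follow the primary method, and the subgroup analyses (Table 5) name the same Cox model, so the wording carries over to them.

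**The concern.** Read word for word, *cluster* modifies *variables*, and the model adjusts for prognostic variables only. That matters in this design. With crossover at 10, 20, 30 and 40 weeks, the four clinics in a batch spend about 80, 60, 40 and 20% of five equal periods under treatment, so treatment is partly confounded with clinic. With 8, 12 or 16 clusters in all, chance differences between clinics enter the treatment estimate, and a model without cluster understates its standard error.

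The second gap does not depend on punctuation. In every batch all clinics start in usual care and end under treatment, so any change in emergency-visit risk over calendar time looks like a treatment effect unless the model has a time term. Both points concern the primary test.

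**Working it through.** **Inputs (Section 5.0 and Table 2).** "a 10% prevalence rate in the treatment group, a 14.8% prevalence rate in the control group"; two-sided 5% test and 80% power; ICC 0.05, with 0.005, 0.01 and 0.1 also tabulated; four sequences, five periods, one cluster per sequence. Sizes: "1880 patients (cluster size of 47 patients per period) for two batches", 1800 (30 per period) for three batches, 1760 (22 per period) for four.

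**1. The plan's own figure.** Generalised least squares on cluster-period means, with exchangeable ICC 0.05, binomial variances (0.148 × 0.852 and 0.10 × 0.90), a z-test and no period effects, gives required totals of 1840 / 1800 / 1760 against the stated 1880 / 1800 / 1760. Power at the stated sizes is 80.9% / 80.5% / 80.4%. The sample size is reproduced to within 3%.

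**2. Type I error if cluster is left out (analytic, no secular trend).** Half of the cluster-periods are treated, so the naive variance per unit outcome variance is 4/N. With treated shares p = 0.8, 0.6, 0.4, 0.2 and B batches, each cluster enters the difference in means with weight (2p − 1)/(2B). The squared weights sum to B × 0.8/(4B²) = 0.2/B. So

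- true variance = ρ × 0.2/B + (1 − ρ) × 4/N
- type I error = 2 × [1 − Φ(1.96 / √(true/naive))]

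At ρ = 0.05:

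| Batches | N | True variance | Naive variance | SE ratio | Type I error |
|---|---|---|---|---|---|
| 2 | 1880 | 0.00500 + 0.00202 = 0.00702 | 0.00213 | 1.82 | 28.1% |
| 3 | 1800 | 0.00333 + 0.00211 = 0.00544 | 0.00222 | 1.57 | 21.1% |
| 4 | 1760 | 0.00250 + 0.00216 = 0.00466 | 0.00227 | 1.43 | 17.1% |

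Over the other ICCs in Table 2 the same formula gives, for 2 / 3 / 4 batches:

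- ICC 0.005: 7.7 / 6.7 / 6.2%
- ICC 0.01: 10.5 / 8.4 / 7.5%
- ICC 0.1: 40.8 / 32.1 / 26.6%

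**3. Simulation of the time-to-event test.** Null trials with 14.8% risk, beta-distributed cluster risks, ICC 0.05, exponential times censored at six months, and the log-rank (Cox score) test:

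- Cluster ignored: 28.2 / 21.4 / 16.2% (2000 trials each) and 26.3 / 20.9 / 17.1% (3000 trials each, 10% dropout).
- Stratified by cluster: 5.6 / 6.1 / 5.0% and 4.7 / 4.7 / 4.8%.

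**4. Cluster handled, period not.** Same set-up without dropout, stratified by cluster, no treatment effect, 2000 trials each. The hazard falls by a fixed fraction from one period to the next. The size of the trend is an assumption; the protocol gives none.

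| Fall per period | 2 batches | 3 batches | 4 batches |
|---|---|---|---|
| 0% | 5.1% | 4.6% | 6.0% |
| 5% | 14.8% | 15.2% | 15.4% |
| 10% | 42.0% | 39.7% | 41.0% |

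**5. Price of period adjustment.** Adding a separate effect for each period in each batch to the calculation in step 1 raises the standard error by a factor of 1.57. Power at the stated sizes falls to about 44% (43.8 / 43.4 / 43.6%).

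**The case against.** The strongest reply is that the protocol nearly answers the question itself. Pre-injury work status is a participant characteristic, and Table 5 uses it as a participant subgroup, so *cluster* has no sensible function as a modifier. The opioid sentence shows the phrase intact. The sample size rests on an ICC. A dropped comma is therefore the likeliest explanation, and it may have been lost when the PDF was read. Section 6.0 also calls this part a brief overview ahead of a SAP, and the choice between stratum, frailty and fixed effect is ordinary SAP content. Nor is every secondary model clearer: Table 4 gives the negative binomial model for missed visits no cluster term at all.

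Most of this stands. A reader might infer that clustering will be ignored, or that the trial has a false-positive rate of 16 to 28%. The document supports neither. Those figures describe a model without cluster at ICC 0.05, and the sentence does contain the word *cluster*.

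Two things remain. The protocol chose to state the covariate list of its primary model, and stated it so that the key term is unclear. And restoring the comma does not supply a time term: the list contains none on either reading.

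**Conclusion.** The point holds as a defect of specification in the primary analysis, not as proof of a wrong analysis. Cluster is probably intended but not clearly stated, and calendar time is not listed.

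If cluster were omitted, type I error would be about 28 / 21 / 16 to 17% for two / three / four batches at ICC 0.05, and about 6 to 41% over the ICCs in Table 2. This assumes one constant ICC across periods, equal cluster-period sizes and no secular trend. With cluster stratified and no trend it is about 5%. With cluster stratified and an untreated trend of 5 to 10% per period, it is about 15 to 40%; this depends wholly on the assumed trend.

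A reader might also infer from the 44% in step 5 that the trial is underpowered. That does not follow from this point alone. It applies to the most generous time adjustment, a free effect for every batch-period. A model with fewer time parameters nested within that one, such as a linear trend, cannot cost more. The figure shows why the time term should be chosen together with the sample size.

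**What to change.** Restate the sentence in Section 6.1 along these lines: a Cox proportional hazards model with treatment, cluster as its own term (fixed effect, stratum or shared frailty, to be chosen in the SAP), terms for batch and calendar period, and the pre-specified prognostic covariates. Say in Section 6.2 and Table 5 that the Cox sensitivity and subgroup analyses use the same structure. Section 6.2 also refers to stratification variables that the protocol does not define; naming cluster and batch would settle that.

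The edit needs no new data, because cluster and enrolment date are known for every participant. If cluster was always intended, that part only confirms it. The real cost is precision from the period terms: the sponsor should choose their form in advance and confirm the power of Section 5.0 under that model.
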